8.3 Photography

Photographs for the study may be taken only at an investigators site as designated by the sponsor. Written training regarding study related photography will be provided during site initiation visits (where applicable).

9. Schedule of Study Activities

Subjects must meet all screening criteria as assessed by subject interview and through examination of facial volume loss. Please refer to the following schedule for additional details:

1. Discuss with each subject his/her willingness to participate in the study and obtain Informed Consent/HIPAA.
2. Inclusion/Exclusion Criteria
3. Document Subject Demographic Information
4. Subject Photography
 - a. To be conducted at baseline prior to first injection and 3 month and 6 month post initial injection. Photography instructions to be provided in a separate study document.
5. Facial volume loss assessment by Investigator and subject
 - a. Investigator/Subject Facial Volume Loss Global Assessment
6. Subjects will receive 1 vial of poly-L-lactic acid reconstituted in the usual sterile fashion with 7cc of sterile water and 2cc of Lidocaine without epinephrine. The contents of the vial will be injected as deemed appropriate by the certified injector and agreed upon by the study subject.
7. Approximately 4-6 weeks later, a second vial will be reconstituted as above and injected according to the above parameters.
8. Approximately 4-6 weeks later (8-12 weeks after the first injections), subjects will be evaluated and a decision jointly made with the injector regarding whether a third vial is desired and appropriate.
9. Injection sites will be prepared in the usual sterile fashion and sites will have Lidocaine topical application 30-90 minutes before the procedure.
10. All subjects will receive full informed consent and will have time for any questions before procedures are initiated.
11. Explicit post procedure instructions will be provided as per usual protocol.
12. Subjects will be instructed to contact the study site immediately with any concerns after each injection session.
13. QOL and Self-Esteem measures by subject
 - a. To be completed 3months and 6 months post initial injection.

10. Early Discontinuation/Withdrawal

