It is the right and duty of the Investigator to discontinue a subject's participation when the subject's health or well-being is threatened by continuation in the study. Such subjects should be withdrawn from the study. In the event of premature discontinuation, the Investigator should determine the primary reason for discontinuation. Subjects may voluntarily withdraw from the study at any time without jeopardy to future medical care. For any subject who withdraws from the study the date and reason for withdrawal will be recorded on the CRF.

11. Compliance with Protocol

The Investigator is responsible for compliance with the protocol at the investigational site. A representative of the Sponsor will make contact with the Investigator and his/her research staff to obtain completed CRFs.

12. Study Termination

If conditions arise during the study that indicate that the study or an investigational site should be terminated, the Sponsor, Investigator, Monitor, IRB, and/or regulatory agencies will discuss the situation and take appropriate action after consultation.

Conditions warranting termination of the study or site include, but are not limited to:

- The decision on the part of the Sponsor to suspend or discontinue evaluation, or development of the study.
- Failure of the Investigator to comply with pertinent national or state regulations, IRB-imposed conditions, or protocol requirements;
- Submission of knowingly false information from the Investigator to the Sponsor, IRB, or any regulatory agency.

13. General Statistical Analysis Methods

Relevant subject information i.e. demographics, facial volume restoration questionnaire answers will be collected and analyzed. This data will be summarized using descriptive statistics.

14. Administrative Issues

This protocol will be conducted in accordance with the applicable U.S. Food and Drug Administration (FDA) regulations and guidelines and Good Clinical Practice (GCP), i.e., the International Conference on Harmonization (ICH) Guideline on Good Clinical Practice.

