14.3.1 Source Documents

Individual subject records will be maintained in the Investigator's Source Documents (SDs). Source documentation is generally considered to be the document on which the information or data point was first recorded. SDs may include a subject's medical records, hospital charts, clinic charts, and the Investigator's study files as well as the results of diagnostic tests such as X-rays, laboratory tests, and electrocardiograms. The Investigator's copy of the CRF may also serve as part of the Investigator's source record for a subject's study-related data. The following information should be entered into the subject's medical record:

- a. Subject's name
- b. Subject's contact information
- c. The date that the subject entered the study and the subject number assigned
- d. The study title and/or the protocol number of the study and the Sponsor's name (Yardley Dermatology Associates, PC)
- e. A statement of the informed consent process and the date that informed consent and HIPAA authorization were obtained.
- f. Records of previous and current dermatological treatments and/or therapies
- g. Dates of all subject visits
- h. The date the subject exited the study, and a notation as to whether the subject completed the study or reason for discontinuation

Study-specific information, such as Investigator and subject effectiveness and safety assessments may be recorded directly on the CRF. With no prior written or electronic record, these data are considered to be source data and will be maintained in the Investigator's study files. Pertinent records related to the study, e.g., the subject's medical chart, will be made available to the Sponsor representative on request with due precaution to protect the privacy of the subject. Personal identifying information (except subject initials) will be redacted on any photocopies of relevant medical records and replaced with the unique Subject Number before submission to the Sponsor. The Investigator will protect the confidentiality of all subjects' records within applicable federal, state and local laws.

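### Section 10 does not separate stopping injections from leaving follow-up, so, read literally, it drops subjects harmed after vial 1 from both questionnaire summaries

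*Combined protocol and SAP*

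**What the plan says.** **Section 10.** The investigator must end participation when a subject's "health or well-being is threatened by continuation in the study". The instruction that follows is "Such subjects should be withdrawn from the study". For anyone who withdraws, "the date and reason for withdrawal will be recorded on the CRF". No exit questionnaire or later form is described.

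**Section 9, injections.** Item 6 gives vial 1 and leaves its use to the injector's judgement and the subject's agreement. Item 7 reads "Approximately 4-6 weeks later, a second vial will be reconstituted as above and injected according to the above parameters". Item 8 makes only the third vial an explicit choice: "a decision jointly made with the injector regarding whether a third vial is desired and appropriate". Item 12 tells subjects to "contact the study site immediately with any concerns after each injection session".

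**Section 9, forms.** Item 13a times the quality-of-life and self-esteem measures: "To be completed 3months and 6 months post initial injection". It sets no minimum number of vials. Section 2 gives the same two time points. The synopsis differs: it places the questionnaire one month after injection two or three.

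**Section 13.** Questionnaire answers are summarized descriptively. There is one treated group of 50 (Section 5.1) and no rule for missing forms.

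**The concern.** Stopping a treatment and leaving a study are different events, and Section 10 treats them as one. Item 12 invites subjects to report problems after each session, so harm from vial 1 can come to light before vial 2 is due. If the investigator then applies Section 10 as written, the subject leaves before either form is due and contributes nothing to the summaries.

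That loss is related to outcome. A subject removed because treatment harmed them would plausibly answer less favourably than one who finished, so their absence tilts the 3- and 6-month summaries towards benefit. There is no control group in which a similar loss might offset it. The tilt runs in the direction the study hopes to show: Objective 1 is the improvement produced by treatment, and Objective 3 is to support its value.

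**Working it through.** The plan gives no figure on this point to reproduce. The check is a comparison of texts, followed by an illustration on assumed values.

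**1. Is there a written route for a one-vial subject to stay in follow-up?**

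| Place | Bearing on a subject harmed after vial 1 |
|---|---|
| Section 10 | Withdrawal from the study; date and reason recorded |
| Section 9 items 6 and 7 | Injector judgement and subject agreement carry over to vial 2; nothing on later forms |
| Section 9 item 8 | Choice to decline, but for vial 3 only |
| Section 9 item 13a | Forms timed from the first injection; a one-vial subject fits |
| Synopsis | Questionnaire timed from injection two or three; a one-vial subject has no time point |
| Appendix 1 | Allows for one or more injections and records the number of treatments; a one-vial subject can complete it |

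The forms can accept such a subject. No section says that the subject should complete them, and the synopsis points the other way.

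**2. When does the gap apply?** Section 10 operates throughout, but from item 8 onwards a subject has a written way to decline treatment and remain. The exposed window is therefore mainly from vial 1 to vial 2, weeks 0 to 4-6. With 3 months taken as about week 13, that window closes 13 − 6 = 7 to 13 − 4 = 9 weeks before the first form.

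**3. How large could the effect be?** All score inputs and withdrawal counts below are assumed. On Appendix 1, 4 means no change. Lower is better for 35 − 2 = 33 items; items 23 and 32 run the other way. The figures apply to the 33.

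*Item mean.* Let k of 50 subjects be withdrawn, completers average 2.5, and withdrawn subjects would have averaged 4 to 6. Shift = (k/50) × (withdrawn mean − 2.5).

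- k = 1: the full-cohort mean is (49 × 2.5 + 4)/50 = 2.53 to (49 × 2.5 + 6)/50 = 2.57. The completers' 2.5 is too favourable by 0.03 to 0.07.
- k = 2: (48 × 2.5 + 8)/50 = 2.56 to (48 × 2.5 + 12)/50 = 2.64. It is too favourable by 0.06 to 0.14.
- If withdrawn subjects would have scored like completers, the shift is 0.
- For scale, a gap of 2 points with 5 of 50 withdrawn gives (5/50) × 2 = 0.20, and with 10 of 50 gives 0.40. Nothing in the documents suggests counts that high.

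*Percent improved.* If a share p of completers score as improved and none of the withdrawn would, overstatement = p × k/50.

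- k = 1: 0.70/50 = 1.4 points to 0.90/50 = 1.8 points.
- k = 2: 2.8 to 3.6 points.

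**The case against.** A reader might infer that the protocol obliges the investigator to lose these subjects' data. The documents do not support that, for three reasons.

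- Item 7 brings item 6's injector judgement and subject agreement forward to vial 2. That wording mainly governs how a vial is injected and is weaker than the explicit choice in item 8, but it gives a basis for holding vial 2 without invoking Section 10.
- The Section 10 trigger is a threat from continuing in the study, not harm from vial 1 as such. Filling in a form ordinarily poses no threat, so once vial 2 is held the trigger need not be met. Section 10 also does not prohibit later forms.
- A reader might take Section 14.3.1 item h, which asks for "a notation as to whether the subject completed the study or reason for discontinuation", as evidence that there is no place for a subject who stopped injections but stayed. It is not. A one-vial subject who returned both forms could be entered there as having completed, and Appendix 1 already records treatment dates and the number of treatments.

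It can also be said that the effect is negligible: few subjects, wholly assumed scores, and no test, power or error rate to disturb.

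These points stand, and they limit the finding to a default that a careful investigator could avoid. They do not remove it. The discretion in items 6 and 7 does not mention the later forms, the only action Section 10 writes down is withdrawal, and with two sites an unwritten alternative may be applied differently at each.

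**Conclusion.** The point holds in a limited form. Section 10 merges stopping injections with leaving follow-up. Applied literally, it removes subjects harmed after vial 1 from both the 3- and 6-month summaries, and the synopsis timing adds to the gap. The direction is probably favourable to treatment, on the assumption that such subjects would answer less favourably than completers.

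The size cannot be estimated from the documents. It is likely small: 0.03 to 0.14 points on an item mean, or 1.4 to 3.6 percentage points improved, for 1 or 2 of 50 under the assumed scores. A reader might infer that the study's conclusion is at risk. Shifts of this size would not by themselves reverse a descriptive conclusion. This is a cheap improvement, for consideration.

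**What to change.** In Section 10:

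- State that when the threat comes from further injections, injections stop but a willing subject stays in follow-up, completes the 3- and 6-month forms timed from the first injection, and is included in the summaries.
- Keep full withdrawal for withdrawn consent, lost contact, or harm from follow-up itself.

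In the report, give the number of subjects stopped for harm. In the synopsis, replace the timing from injection two or three with that of Section 9 item 13a, so that a one-vial subject has a time point throughout.

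The cost is a sentence or two in Section 10, one line in the synopsis, a few extra follow-up contacts, and possibly a slightly less favourable average. The change does not address voluntary withdrawal or lost contact, for which Section 13 would still have no missing-data rule.

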14.1 Protection of Human Subjects

14.1.1 Compliance with Informed Consent Regulations (21 CFR Part 50)

Written informed consent will be obtained from each subject prior to enrollment into the study, i.e., before performing any screening evaluations or questionnaire completion.

14.1.2 Compliance with Institutional Review Board Regulations (21 CFR Part 56)

This study will be conducted in accordance with IRB regulations (U.S. 21 CFR Part 56.103). The Investigator must obtain approval from a properly constituted IRB prior to initiating the study. Yardley Clinical Research Associates is to be notified immediately if the responsible IRB has been disqualified or if proceedings leading to disqualification have begun.

14.1.3 Compliance with the Principles of Good Clinical Practice (ICH E6)

This protocol will be conducted in accordance with the applicable Good Clinical Practice (GCP) regulations and guidelines (ICH E6).

No amendments to the protocol will be implemented without the prior written consent of the Sponsor. Should an amendment be necessary, the reviewing IRB may require review and approval prior to implementation.

14.2 Subject Confidentiality

A report of the results of this study may be published, but the subject's name will not be disclosed in this document. The subject's name may be disclosed to the Sponsor of the study (Yardley Clinical Research Associates), the governing health authorities, or the FDA (U.S. Food and Drug Administration) if they inspect the study records. Appropriate precautions will be taken to maintain confidentiality of medical records and personal information.

14.2.1 Subject Privacy

Written authorization will be obtained from each subject prior to enrollment into the study in accordance with the applicable privacy requirements [e.g., the Health Insurance Portability and Accountability Act Standards for Privacy of Individually Identifiable Health Information ("HIPAA")].

14.3 Required Regulatory Documents

It is the responsibility of the Investigator and study staff to maintain a comprehensive and centralized filing system of all study-related documentation, which is suitable for inspection at any time either by the IRB or FDA. Elements should include:

- Subject files containing the completed case report forms, supporting source documentation and the informed consent, with signatures by the Investigator or sub-Investigators.
- Confidential disclosure agreement with the sponsor.
- Financial disclosure forms for each Investigator or sub-Investigator.
- Study files, containing the following required documentation:
 - Protocol with all amendments
 - Copies of all pre-study documentation and all correspondence to and from the IRB and the sponsor or sponsor representatives
 - An up-to-date curriculum vitae for the principal Investigator.
 - Signed and dated Investigator agreement
 - Assurance that the reviewing IRB complies with the requirements set forth in Title 21 Part 56 of the CFR. The required documentation will consist of the name and address of the IRB and a list of its members, including their titles, occupations, and any institutional affiliations, or a DHHS Assurance number.
 - A copy of the formal written notification regarding approval of the protocol by the IRB.
 - A copy of the IRB approved informed consent form and other adjunctive materials (e.g., advertising) used in the study, including written documentation of IRB approval of these items.
 - In addition to the documents required prior to the study, other documentation may be required during the course of the study.

14.3.1 Source Documents

Individual subject records will be maintained in the Investigator's Source Documents (SDs). Source documentation is generally considered to be the document on which the information or data point was first recorded. SDs may include a subject's medical records, hospital charts, clinic charts, and the Investigator's study files as well as the results of diagnostic tests such as X-rays, laboratory tests, and electrocardiograms. The Investigator's copy of the CRF may also serve as part of the Investigator's source record for a subject's study-related data. The following information should be entered into the subject's medical record:

- a. Subject's name
- b. Subject's contact information
- c. The date that the subject entered the study and the subject number assigned
- d. The study title and/or the protocol number of the study and the Sponsor's name (Yardley Dermatology Associates, PC)
- e. A statement of the informed consent process and the date that informed consent and HIPAA authorization were obtained.
- f. Records of previous and current dermatological treatments and/or therapies
- g. Dates of all subject visits
- h. The date the subject exited the study, and a notation as to whether the subject completed the study or reason for discontinuation

Study-specific information, such as Investigator and subject effectiveness and safety assessments may be recorded directly on the CRF. With no prior written or electronic record, these data are considered to be source data and will be maintained in the Investigator's study files. Pertinent records related to the study, e.g., the subject's medical chart, will be made available to the Sponsor representative on request with due precaution to protect the privacy of the subject. Personal identifying information (except subject initials) will be redacted on any photocopies of relevant medical records and replaced with the unique Subject Number before submission to the Sponsor. The Investigator will protect the confidentiality of all subjects' records within applicable federal, state and local laws.

14.3.2 Case Report Form (CRF) Completion

The Investigator is responsible for ensuring that data are properly recorded on each subject's CRFs and related documents. The Investigators must sign the protocol signature page and will personally sign where indicated on the respective CRF pages to certify that the observations and findings are recorded on the CRFs correctly and completely. All required data will be recorded on the CRFs for this study, which will be designed and provided by the Sponsor.

All CRF entries must be in ink; black is preferred. An error will be corrected by a single line drawn through it, and the correct data, recorder's initials and correction date will be entered adjacent to the error. All errors must remain legible. Erasure or obliteration of errors on the CRF or other permanent study record is strictly prohibited.

The reason for any missing CRF data will be explained:

- a. Not performed or not done = ND
- b. Cannot be determined or approximated, unknown = UNK or UN
- c. Does not apply, not applicable = NA
- d. No data are available = NAV

Copies of the CRF pages will be collected by the Sponsor after review and verification of the completion and accuracy of the study data. As needed, the Investigator will be contacted to clarify illegible or incomplete CRF entries.

14.3.3 Retention of Documentation

Essential documents are any records that demonstrate the compliance of the subject, Investigator, Sponsor, and Monitor with the study protocol, with standards of Good Clinical Practice (GCP), and with all applicable regulatory requirements. Essential documents (including but not limited to study-related correspondence, subject records, subject privacy documentation, records of the distribution and use of all investigational devices, and copies of CRFs should be retained and available for audit by the Sponsor's auditor and regulatory authorities until at least 2 years after completion or termination of the study. It is the responsibility of the Sponsor to inform the Investigator when these documents no longer need to be retained

14.4 Proprietary Information

The information generated during this study is considered to be the property of the Sponsor, and cannot be used in publication without the written consent of the Sponsor.

14.5 Publications

Sponsor-Investigator retains the right to publish study findings in the venue of its choice.

APPENDIX 1: Facial Volume Restoration Outcome Questionnaire

Site # _____ Subject # _____

Date: _____

Treatment visit 1 date: _____

Sex: Female Male

Treatment visit 2 date: _____

Age: 35-45 45-60 60-75

Treatment visit 3 date: _____

City/Country of residence: _____

Number of Poly-L-Lactic Acid treatments: _____

Please circle the number that best describes how you feel. Circling the number one suggests that you believe that the description on the left hand column best describes how you feel. Circling the number 7 suggests that you believe that the description on the right hand column best describes how you feel. Circling number 4 suggests that you feel that there has been no change. Please be honest.

Since my Poly-L-Lactic Acid injection (s), I find that I am in general...

1. Less anxious	1 2 3 4 5 6 7	More anxious
2. More optimistic	1 2 3 4 5 6 7	Less Optimistic
3. More energetic	1 2 3 4 5 6 7	Less energetic
4. Eating more healthy food	1 2 3 4 5 6 7	Eating less healthy food
5. Happier	1 2 3 4 5 6 7	Sadder
6. Exercising more	1 2 3 4 5 6 7	Exercising less
7. Less irritable	1 2 3 4 5 6 7	More irritable
8. More amorous	1 2 3 4 5 6 7	Less amorous
9. More social	1 2 3 4 5 6 7	Less social
10. More productive	1 2 3 4 5 6 7	Less productive
11. More focused	1 2 3 4 5 6 7	Less focused
12. Less tired	1 2 3 4 5 6 7	More tired
13. Less angry	1 2 3 4 5 6 7	More angry
14. More confident	1 2 3 4 5 6 7	Less confident
15. More sexually confident	1 2 3 4 5 6 7	Less sexually confident
16. More assertive	1 2 3 4 5 6 7	Less assertive
17. Less argumentative	1 2 3 4 5 6 7	More argumentative
18. More comfortable with others	1 2 3 4 5 6 7	Less comfortable with others
19. More likely to go out	1 2 3 4 5 6 7	Less likely to go out
20. More involved in community activities	1 2 3 4 5 6 7	Less involved in community activities
21. Doing better at work/school	1 2 3 4 5 6 7	Doing worse at work/school
22. More in control	1 2 3 4 5 6 7	Less in control
23. Taking more medications	1 2 3 4 5 6 7	Taking less medications
24. Less depressed	1 2 3 4 5 6 7	More depressed
25. Seen by others as less stressed	1 2 3 4 5 6 7	Seen by others as more stressed
26. Feeling more attractive	1 2 3 4 5 6 7	Feeling less attractive

27. More relaxed	1 2 3 4 5 6 7	Less relaxed
28. Happier when looking in mirror	1 2 3 4 5 6 7	Less happy looking in mirror
29. Using less cosmetics to hide defects	1 2 3 4 5 6 7	Using more cosmetic to hide defects
30. Happier when my face is touched	1 2 3 4 5 6 7	Less happy when my face is touched
31. My life is better	1 2 3 4 5 6 7	My life is worse
32. Drinking more alcohol	1 2 3 4 5 6 7	Drinking less alcohol
33. Happier with my body	1 2 3 4 5 6 7	Less happy with my body
34. More in control of my eating	1 2 3 4 5 6 7	Less in control of my eating
35. More content	1 2 3 4 5 6 7	Less content

Thank you for your time and honesty.

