5.1 Number of Subjects

50 male and/or female subjects 35 years of age or older who meet the protocol's participant eligibility requirements will be enrolled in the study at 2 investigational sites.

Study sites will be selected on the basis of experience in facial volume restoration and anticipated subject enrollment rate, with the objective of completing enrollment within approximately 2 months.

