8.2 Subject Self- Report Quality of Life Instrument

A subject self-report instrument with 35 questions will be distributed to the subject for completion at the study site. This questionnaire is designed to assess the emotional and functional impact of facial acne scarring.

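### Questionnaire item 21 (work/school) has no 'does not apply' answer, so a 4 from a subject with no work or school cannot be told from a true 'no change'

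*Combined protocol and SAP*

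**What the plan says.** Section 8.2 describes the instrument: "A subject self-report instrument with 35 questions will be distributed to the subject for completion at the study site". In Appendix 1 every item is a row of numbers from 1 to 7 between two opposed descriptions. At the low end, "Circling the number one suggests that you believe that the description on the left hand column best describes how you feel". At the midpoint, "Circling number 4 suggests that you feel that there has been no change". The form has no not-applicable box and no instruction for an item that does not fit the subject's circumstances.

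Item 21 has "Doing better at work/school" on the left and its opposite on the right. Section 5.1 plans "50 male and/or female subjects 35 years of age or older". Sections 5.2 and 5.3 set no requirement about employment or schooling, and the age bands at the head of the form run to 60-75.

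Section 14.3.2 asks for a reason for any missing CRF data and lists codes, among them "Does not apply, not applicable = NA". Section 13 plans descriptive statistics of the questionnaire answers. It defines no total score, no denominator for each item and no rule for skipped or inapplicable items.

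Sections 2 and 9 have the questionnaire completed at 3 and 6 months after the first injection. (The Synopsis gives a different timing, one month after the second or third injection. The between-visit part of this point applies to the schedule in Sections 2 and 9.)

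**The concern.** A retired subject, or one otherwise without work or school, has no performance to rate on item 21. The likely responses are to leave it blank or to circle the neutral number. A circled 4 enters the data as a genuine report of no change. Nothing on the form records employment. Section 9 calls for demographic information without listing its content, so the two kinds of 4 may not be separable afterwards.

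The item-level result is what is at stake. Section 13 promises a summary of questionnaire answers and no score, so individual items are what a reader will see. Item 21 speaks directly to the functional part of Objective 1. For that objective the structural 4s understate any shift. For Objective 2, on stability, they work the other way: a subject who circles 4 at both visits because the item does not apply looks perfectly stable.

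**Working it through.** The plan states no expected score, effect size, power or sample-size derivation, so there is no figure of its own to reproduce.

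**Inputs from the documents:** scale 1 to 7 with 4 as no change (Appendix 1); 35 items (Section 8.2); 50 subjects (Section 5.1).

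**Assumed inputs:** p, the share of respondents to whom item 21 does not apply and who circle 4; m, the item mean among those to whom it applies. The documents give neither. I take m = 2.5, a 1.5-point shift toward the favourable left side, and p = 0.2, 0.4 and 0.6.

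**1. Item mean when the share p circles 4.** Observed mean = 4p + (1-p)m = 4 + (1-p)(m-4), so the observed shift is (1-p) times the applicable shift.

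| p | observed shift | observed mean |
|---|---|---|
| 0.2 | 0.8 × 1.5 = 1.2 | 2.8 |
| 0.4 | 0.6 × 1.5 = 0.9 | 3.1 |
| 0.6 | 0.4 × 1.5 = 0.6 | 3.4 |

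**2. Item mean when the share p skips.** The mean stays at m. Only the number answering falls, to 50(1-p): 40, 30 or 20 of 50.

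**3. Change from 3 to 6 months.** If the same subjects circle 4 at both visits, observed change = [4 + (1-p)(m6-4)] - [4 + (1-p)(m3-4)] = (1-p)(m6-m3). An assumed loss of 0.5 points would appear as 0.4, 0.3 or 0.2.

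**4. Effect on a 35-item mean.** None is planned. If one were formed with all items scored in the same direction, item 21 would move it by p × 1.5/35. At p = 0.6 this is 0.9/35 = 0.026 points. If items 23, 29 and 32 were diluted equally as well, the movement would be 4 × 0.9/35 = 0.10 points.

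**5. Does the same problem reach items 23, 29 and 32?** These ask about change in behaviour since the injections: medication, "Using less cosmetics to hide defects" and "Drinking more alcohol". A subject who did not use the product before and does not use it now has not changed, so 4 is a true answer. The whole-sample mean is then the correct average change. What cannot be recovered is the change among users, because the form does not identify them. Item 21 differs: without work or school there is no status that could have stayed the same.

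**6. Does Section 14.3.2 resolve it?** Its codes explain missing data. A blank item 21 can be coded as not applicable. A circled 4 is not missing, so no code is triggered.

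**The case against.** The strongest reply is that the plan already offers a route. Section 8 says subjects will be trained on the scale, Section 8.2 has it completed at the site, nothing on the form forbids a blank, and Section 14.3.2 supplies a code for it. Staff could tell a retired subject to leave item 21 empty. This stands in part: it means subjects are not forced to circle 4. But no document tells staff to do so, and once a 4 is circled the information is lost.

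The second reply is about size. One item of 35 is affected, the inputs are assumed, and for Objective 1 the error runs toward no effect, so it cannot manufacture a benefit. All of this stands and sets the weight of the point. It does not make the item-level summary interpretable, and the direction is less reassuring for Objective 2.

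The third reply is comparability. Section 2 describes the questionnaire as already used in other filler studies, and altering the response format weakens the link. This is a real but small cost, dealt with under the fix.

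A reader might also infer three stronger claims that the documents do not support:
- That skipping pulls an item toward no effect. It would do so only if blanks were imputed as 4, and no imputation is planned.
- That non-drinkers and people who use no cosmetics or medication have no valid answer. For a continuing non-user, 4 is truthful. Restricting to users answers a different question, which the protocol does not pose.
- That functional benefit will look weaker than emotional benefit. The documents define no such subscales and plan no such comparison. Other functional items, such as exercise, sociability and productivity, do not depend on having a job.

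**Conclusion.** The point holds for item 21 and is minor. The form cannot separate a 4 meaning that performance at work or school did not change from a 4 meaning that there is no work or school to rate, and the not-applicable code does not repair this.

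The item's shift, and any 3-to-6-month change on it, shrink by the factor (1-p). This rests on two assumptions: that affected subjects circle 4 and do not skip, and, for the change between visits, that the same subjects do so both times. The actual p cannot be found from the documents, so the illustrated sizes are not estimates. The consequence is confined to the item-level result. For items 23, 29 and 32 the limitation is only that the effect among users cannot be recovered.

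**What to change.** In Appendix 1, add a box reading 'does not apply to me' beside item 21, keeping its wording and the 1-7 scale. The same box on items 23, 29 and 32 is optional. If added there, it should be for subjects with no use before or since treatment, so that starting or stopping is still scored as change.

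In Section 13, state that:
- item 21 is summarised among subjects to whom it applies, with that number shown at each visit;
- not-applicable answers are left out of any cross-item mean and are not counted as 4;
- for any optional item given the box, the applicable-only summary is shown beside the all-respondent one.

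The cost is a reprint of the form, a short addition to Section 13, smaller denominators on the affected items and a slightly less direct comparison with earlier uses of the questionnaire. Showing an all-respondent summary that counts not-applicable as 4 alongside the main one largely offsets the last. The change is best made before the first questionnaire is completed, because a circled 4 may not be classifiable afterwards.
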